### **6.1.2 Medical history and demographic data**

Medical history includes clinically significant diseases within 10 years, surgeries, cancer history (including prior cancer therapies and procedures), cardiovascular medical history, smoking history, use of alcohol and drugs of abuse, and all medications (e.g. prescription drugs, over-the-counter drugs, herbal/homeopathic remedies, nutritional supplements) used by the patient within 365 days prior to the Screening Visit 1, except for the history of use of corticosteroids for GCA, where all available and related toxicities data should be recorded.

Demographic data will include age, sex, and self-reported race.

### **6.1.3 Height**

Height in centimeters (cm) will be measured at Screening Visit 1.

### **6.1.4 Alcohol test/drug screen**

All patients will be screened for substances of abuse. These assessments will be documented in source records only and will not be entered into the eCRF.

### **6.1.5 Tuberculosis screening**

A central laboratory immunological test (QuantiFERON TB-Plus) must be performed at Screening Visit 2 to screen the patient population for latent tuberculosis infection. The results must be known prior to randomization to determine the patient's eligibility for the study.

Patients with a positive test may participate in the study if further work up (according to local practice/guidelines) establishes conclusively that

- the patient has no evidence of active tuberculosis
- if presence of latent tuberculosis is established then treatment according to local country guidelines must have been initiated.

#### **6.1.5.1 Central laboratory test for tuberculosis screening**

The QuantiFERON TB-Plus test will be analyzed by the central laboratory. Details on the collection, processing and shipment of samples and reporting of results by the central laboratory are provided in the laboratory manual.

## **6.2 Treatment exposure and compliance**

Compliance to the study treatment regimen is ensured by administration of secukinumab/placebo at the study site at all visits as per the study schedule (Table 6-1). Information on the study treatment administration or any deviation from the dose regimen must be recorded in the eCRF. All study treatment dispensed and returned must be recorded in the Drug Accountability Log.

## 6.3 Efficacy

### 6.3.1 Primary efficacy assessment

The primary efficacy objective is to evaluate the efficacy of secukinumab compared to placebo, in combination with a 26-week prednisolone taper regimen, based on the proportion of patients with GCA who have sustained remission.

The primary efficacy endpoint is the proportion of GCA patients in sustained remission (as defined below) at Week 28.

Definition of remission: Absence of flare (see below). Definition of sustained remission: patients without flare (see below) until Week 28 and in adherence to the protocol prednisolone taper regimen.

Definition of flare: Determined by the investigator and defined as the recurrence after remission of signs or symptoms of GCA (see [Section 6.3.1.1](#)) and/or ESR  $\geq 30$  mm/hr (see [Section 6.4.5.5](#)) and/or CRP  $\geq 10$  mg/L (see [Section 6.4.5.4](#)) attributable to GCA.

#### 6.3.1.1 Signs and symptoms of GCA disease

Evaluation of clinical signs and symptoms by the Efficacy Assessor at every study visit according to the schedule of assessment will include the following:

- Fever ( $> 38^\circ$  C).
- Symptoms of polymyalgia rheumatica (PMR) (morning stiffness and/or pain, in the shoulder and/or hip girdles).
- Localized headache, temporal artery or scalp tenderness.
- Visual signs or symptoms such as acute or subacute vision loss due to arteritic anterior ischemic optic neuropathy (A-AION), transient blurry vision (generally monocular or at least affecting one eye at a time, but potentially affecting both eyes).
- Jaw or mouth pain.
- New or worsened extremity claudication.
- Other features judged by the clinician-investigator to be consistent with a GCA or PMR flare.

### 6.3.2 Secondary efficacy assessments

The following secondary efficacy endpoints will be assessed as herein described or described in the respective protocol sections:

- Remission rate at Week 12 ([Section 6.3.1](#))
- Time to first GCA flare after clinical remission (up to Week 52) ([Section 6.3.1](#))
- Total cumulative prednisolone dose up to Weeks 28 and 52 ([Section 9.5.1](#))
- Proportion of GCA patients in sustained remission at Week 52
  - Definition of remission: absence of flare. .
  - Definition of sustained remission: patients without flare until Week 52 and in adherence to the protocol prednisolone taper regimen + prednisolone-free phase from Week 27 onwards.

- Definition of flare: determined by the investigator and defined as the recurrence after remission of signs or symptoms of GCA and/or erythrocyte sedimentation rate (ESR)  $\geq 30$  mm/hr and/or CRP  $\geq 10$  mg/L attributable to GCA.
- Proportion of patients on prednisolone dose  $< 5$  mg/day at Week 19, Week 28 and Week 52 ([Section 9.5.1](#))
- Changes from Baseline in disease activity and quality of life measures at Week 4, 8, 12, 16, 20, 24, 28, 36, 44, 52 for each of the following:
  - PhGA, VAS ([Section 6.5.1.1.1](#))
  - 
  - PROs:
    - PGA, VAS ([Section 6.5.2.1.1](#))
    - FACIT-Fatigue ([Section 6.5.2.1.2](#))
    - SF-36 ([Section 6.5.2.1.3](#))
    - EQ-5D ([Section 6.5.2.1.4](#))
- Change from Baseline at Week 4, 8, 12, 16, 20, 24, 28, 32, 36, 40, 44, 48 and 52 in CRP ([Section 6.4.5.4](#)) and ESR ([Section 6.4.5.5](#)).

All efficacy assessments should be performed prior to administration of study treatment.

A large rectangular area of the page is completely blacked out, indicating redacted content. This redaction covers the majority of the page below the text "All efficacy assessments should be performed prior to administration of study treatment." and extends to the bottom of the page.

### **6.3.6 Appropriateness of efficacy assessments**

The primary efficacy assessment in this study is aligned with the primary efficacy assessment in the GIACTA trial ([Stone et al 2017](#)), which demonstrated the efficacy of another humanized monoclonal antibody (i.e. tocilizumab) in combination with similar corticosteroid tapering (i.e. prednisone) for the treatment of patients with GCA. Other efficacy assessments, including the PhGA and PRO assessments, including PGA are closely aligned with those included in other Phase II and Phase III clinical trials in the clinical development program for secukinumab for other chronic inflammatory diseases.

## **6.4 Safety/tolerability**

Safety assessments are specified below with the assessment schedule detailing when each assessment is to be performed. For details on AE collection and reporting, refer to Section [7](#).

### **6.4.1 Physical examination**

A complete physical examination will include the examination of general appearance, skin, neck (including thyroid), eyes, ears, nose, throat, lungs, heart, abdomen, back, lymph nodes, extremities, vascular, and neurological systems. If indicated based on medical history and/or symptoms, rectal, external genitalia, breast, and pelvic examinations will be performed.

Information for all physical examinations must be included in the source documentation at the study site. Clinically relevant findings that are present prior to signing informed consent must be recorded on the appropriate eCRF that captures medical history. Significant findings made after first administration of investigational drug which meet the definition of an AE must be recorded as an AE.

### **6.4.2 Vital signs**

Vital signs include blood pressure (both arms) and pulse measurements, respiratory rate and temperature. After the patient has been sitting for 5 minutes, with back supported and both feet placed on the floor, systolic and diastolic blood pressure will be measured 3 times per arm using a validated device, with an appropriately sized cuff. The repeat sitting measurements will be made at 1 to 2 minute intervals and the mean of the 3 measurements (per arm) will be used. In case the cuff sizes available are not large enough for the patient's arm circumference, a sphygmomanometer with an appropriately sized cuff may be used. Blood pressure assessments will be performed on both arms.

Clinically notable vital signs are defined in [Appendix 1](#).

### **6.4.3 Weight**

Body weight (to the nearest 0.1 kilogram (kg) in indoor clothing, but without shoes) will be measured.

If possible, body weight assessments should be performed by the same study site staff member using the same scale throughout the study.

#### **6.4.4 Tolerability of investigational treatments**

Tolerability will be assessed by AEs, laboratory values, injection site reaction and immunogenicity. The local tolerability at the site of s.c. injection of the study treatment will be assessed in case of any local reaction, until this has disappeared. The assessment of pain, redness, swelling, induration, hemorrhage and itching will be performed by a physician and will be recorded on the appropriate eCRF capturing AEs, including the severity (mild, moderate, severe) and the duration of the adverse reaction.

#### **6.4.5 Laboratory evaluations**

Clinically relevant deviations of laboratory test results occurring during or at completion of the study must be reported and discussed with Novartis personnel. The results should be evaluated for criteria defining an AE and reported as such if the criteria are met. Repeated evaluations are mandatory until normalization of the result(s) or until the change is no longer clinically relevant. In case of doubt, Novartis personnel should be contacted.

Clinically notable laboratory findings are defined in [Appendix 1](#).

##### **6.4.5.1 Hematology**

Hemoglobin, hematocrit, red blood cell count, white blood cell (WBC) count with differentials and platelet count will be measured.

##### **6.4.5.2 Clinical chemistry**

Serum chemistries will include sodium, potassium, blood urea nitrogen (BUN)/urea, bicarbonate, phosphorous, total protein, calcium, albumin, uric acid, creatinine, creatine kinase, total bilirubin, aspartate aminotransferase (AST), alanine aminotransferase (ALT), gamma glutamyl transferase (GGT) and alkaline phosphatase (ALP); at all time points specified in [Table 6-1](#).

If the total bilirubin concentration is increased above 2 times the ULN, direct and indirect reacting bilirubin should be differentiated.

Follicle stimulating hormone is only done at Screening Visit 2 and only in patients who are not reported post-menopausal at Screening Visit 2.

##### **6.4.5.3 Lipid panel and glucose**

A lipid profile including high density lipoprotein, low density lipoprotein, cholesterol, triglycerides, HbA1c and glucose will be measured from a fasting blood sample.

##### **6.4.5.4 C-reactive protein**

Blood for this assessment will be obtained at the visits indicated in [Table 6-1](#) in order to identify the presence of inflammation, to determine its severity, and to monitor response to treatment.

#### **6.4.5.5 Erythrocyte sedimentation rate**

Blood for ESR, which is helpful in diagnosing inflammatory diseases and is used to monitor disease activity and response to therapy, will be obtained at the visits indicated in [Table 6-1](#). ESR tests will be done locally. For details please refer to the Laboratory Manual.

#### **6.4.5.6 Urinalysis**

Dipsticks will be provided by the central laboratory to the study sites for local urinalysis assessments. Dipstick measurements for standard parameter such as specific gravity, protein, glucose, pH, erythrocytes, hemoglobin, nitrite, bilirubin, urobilinogen, ketones and WBC will be done at scheduled visits as indicated in [Table 6-1](#). If dipstick measurement results are positive (abnormal), results will be captured in the e CRF.

#### **6.4.6 Electrocardiogram**

In this study, electrocardiograms (ECGs) will be performed locally. ECGs must be recorded after 10 minutes rest in the supine position to ensure a stable Baseline. A single 12 lead ECG is collected. The Fridericia QT correction formula (QTcF) should be used for clinical decisions. The original ECGs (on non-heat-sensitive paper or a certified copy on non-heat sensitive paper), appropriately signed, must be collected and archived at the study site. The ECG tracing must be labeled with study number, patient initials, patient number, date and time, and filed in the study site source documents.

Clinically relevant abnormalities should be recorded on the relevant medical history/Current medical conditions eCRF page for the Baseline ECG.

Clinically relevant abnormalities noted after the Baseline ECG should be reported as AE (see [Section 7](#)).

#### **6.4.7 Pregnancy and assessments of fertility**

##### **Pregnancy testing**

Secukinumab must not be given to pregnant women; therefore, effective methods of birth control must be used for women of child-bearing potential (see Exclusion Criteria definitions, [Section 4.2](#)).

A serum  $\beta$ -hCG test will be performed in all women at Visit 2 (Screening 2). All women who are not surgically sterile or in menopause at Screening will have local urine pregnancy tests as indicated in [Table 6-1](#). A positive urine pregnancy test requires immediate interruption of study treatment until serum  $\beta$ -hCG is performed and found to be negative. If positive, the patient must be discontinued from the trial. Additional pregnancy testing might be performed if requested per local requirements. Refer to [Section 7.1.4](#) for details on reporting of pregnancy. Pregnancy test results are kept in the eCRF.

## Assessments of fertility

Refer to [Section 4.2](#) for criteria to determine women that are not of child bearing potential.

Medical documentation of oophorectomy, hysterectomy, or tubal ligation must be retained as source. Subsequent hormone level assessment to confirm the woman is not of child bearing potential must also be available as source documentation in the following cases:

- Surgical bilateral oophorectomy without a hysterectomy.
- Reported 12 months of natural (spontaneous) amenorrhea with an appropriate clinical profile.

In the absence of the above medical documentation, FSH testing is required of any female patient who states that they are of non-child bearing potential, regardless of reported reproductive/menopausal status at Screening/Baseline.

## 6.4.8 Other safety evaluations

### 6.4.8.1 Immunogenicity

Blood samples for immunogenicity (anti-AIN457 antibodies) will be taken pre-dose at the scheduled time points as indicated in [Table 6-1](#). Anti-secukinumab antibodies will be assessed in serum by MSD assay. Details of the analytical methods to assess anti-secukinumab antibodies in serum will be described in the bioanalytical data report.

In addition, if a patient discontinues from the study at any time point, he/she will need to provide a sample at the last visit. The actual sample collection date and exact time will be entered on the Immunogenicity Blood collection eCRF. Sampling problems will be noted in the Comment section of the eCRF.

A laboratory manual will be provided to investigators with detailed information on sample collection, handling and shipment. Tubes and preprinted labels will be provided by the central laboratory to the sites.

The detailed methods for immunogenicity assessment will be described in the Bioanalytical Data Report.

## 6.4.9 Appropriateness of safety measurements

The safety assessments selected are standard for this indication/patient population.

## 6.5 Additional assessments

### 6.5.1 Clinical outcome assessments

#### 6.5.1.1 Clinician reported outcomes

##### 6.5.1.1.1 Physician's global assessment of disease activity

The physician's global assessment of disease activity (PhGA) will be performed using 100 mm VAS ranging from no disease activity to maximal disease activity, after the question "*Considering all the ways the giant cell arteritis affects your patient, please*

*indicate with a vertical mark (|) through the horizontal line how well his or her condition is today".* To enhance objectivity, the physician must not be aware of the specific patient's global assessment of disease activity (PGA), when performing his own assessment on that patient.

The PhGA is filled in by the investigator at all visits specified in [Table 6-1](#) prior to study drug administration.

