## 6.5.2 Patient reported outcomes

The patient should be given the PRO measures to be completed at the scheduled visit before any clinical assessments are conducted. The patient should be given sufficient space and time to complete the PRO measures.

The site personnel (referring to who could be responsible for administering and checking completions of PRO measures) should check PRO measures for completeness and ask the patient to complete any missing responses. The responses stored electronically on the database will be considered the source file.

Completed measures and any unsolicited comments written by the patient should be reviewed and assessed by the investigator for responses, which may indicate potential AEs or SAEs before any clinical study examinations. This assessment should be documented in study source records. If AEs or SAEs are confirmed, study investigators should not encourage the patient to change responses reported in the completed questionnaires. Study investigators must follow reporting instructions outlined in [Section 7](#) of the study protocol.

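### The protocol masks the physician's global rating to the patient's global rating, but its questionnaire review, as written, shows the investigator the patient's rating first

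*Protocol*

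**What the plan says.** Protocol Section 6.5.1.1.1 names the PhGA rater: "The PhGA is filled in by the investigator at all visits specified in" Table 6-1, before study drug is given. To make the rating more objective, it adds that "the physician must not be aware of the specific patient's global assessment of disease activity (PGA), when performing his own assessment".

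Protocol Section 6.5.2 covers all patient-reported outcomes. On timing it says: "The patient should be given the PRO measures to be completed at the scheduled visit before any clinical assessments are conducted". Site personnel administer the forms and check that they are complete. The content review goes to the investigator: "Completed measures and any unsolicited comments written by the patient should be reviewed and assessed by the investigator for responses", specifically responses "which may indicate potential AEs or SAEs before any clinical study examinations". That review is to be documented in source records.

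The PGA VAS is Section 6.5.2.1.1, so it is one of these measures. Section 6.3.6 and Table 2-1 also class it as a patient-reported outcome. The opening bullets of Section 6 have every questionnaire finished before the patient sees the investigator.

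**The concern.** The two sections give the same role incompatible instructions. One keeps the PGA from the investigator while the PhGA is scored. The other routes every completed questionnaire, the PGA included, to the investigator before the examination starts.

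What is at stake is the independence of the PhGA. The protocol treats PhGA and PGA as separate secondary endpoints, one from the clinician and one from the patient, and the sponsor thought the separation important enough to write a masking rule. A physician who has just read the patient's mark may move towards it. Sites may also settle the conflict in different ways, so that some PhGA ratings are masked and others not. The documents do not ask for a record of which was done.

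**Working it through.** The protocol gives no figure to reproduce here. The check sets the instructions side by side and then counts the ratings involved.

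**Who does what, and when**

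| Step | Who | When | Source (protocol) |
|---|---|---|---|
| Patient completes all questionnaires, PGA included | Patient | Before seeing the investigator | Sections 6 and 6.5.2 |
| Completeness check | Site personnel | After completion; no exact time given | Section 6.5.2 |
| Content review for possible adverse events | Investigator | Before any clinical study examination | Section 6.5.2 |
| PhGA scoring, unaware of the PGA | Investigator | Before study drug; no order relative to the content review | Section 6.5.1.1.1 |

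**Is there a way out in the text?** Three provisions would remove the conflict:

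1. *The PGA is left out of the content review.* Section 6.5.2 refers to completed measures without exception.
2. *The two tasks go to different people.* Both sections name the investigator. The Efficacy Assessor of Section 6.3.1.1 is tied only to clinical signs and symptoms. Section 5.4 mentions persons performing assessments, and Section 6.5.2.1.2 mentions a treating physician, but neither is linked to the PhGA or to the questionnaire review.
3. *The PhGA is scored before the content review.* No section says so. It would mean a global rating of disease activity made before the examination.

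None of the three is present.

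**How many ratings**

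- Visits in Table 6-1 that carry both scales, to Week 28: Baseline and Weeks 4, 8, 12, 16, 20, 24, 28 = 8.
- After Week 28: Weeks 36, 44, 52 = 3.
- Total: 8 + 3 = 11 visits.
- Planned patients (protocol Section 4): 50.
- Upper bound: 11 × 50 = 550 scheduled PhGA ratings.

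Neither scale is scheduled at Weeks 1, 2, 3, 32, 40, 48, 56 or 60.

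**What the ratings feed.** SAP Section 2.7.2 reports PhGA by descriptive statistics for change and relative change from baseline. The primary endpoint (SAP Section 2.5.1) and the criteria for continuing development (SAP Section 2.5.2) do not use it.

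**The case against.** The best defence is that the two rules differ in force and scope. The masking rule is a specific prohibition about one instrument. The review rule is a general recommendation, worded with *should*, aimed at adverse events. On ordinary reading the specific prohibition limits the general advice, and a careful site could comply with both by setting the PGA aside or by using two physicians. This stands in part: a reader might infer that the masking is impossible to keep, and the documents do not support that. They do not, however, tell sites to take either route, and the documented default procedure leads to unmasking.

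Two further inferences are tempting and should not be drawn.

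- *The masking fails at every visit.* Only the 11 visits with both scales are affected.
- *The flare decision, and so the primary endpoint, is compromised.* Section 6.3.1 does leave flare to the investigator: "Determined by the investigator and defined as the recurrence after remission of signs or symptoms of GCA", with raised ESR or CRP as further grounds. But the masking rule covers only the PhGA, and no section requires flare to be judged without the PGA. Several of the listed symptoms are reported by the patient, so the patient's account belongs in that judgement. Treatment is double-blind, and nothing in the documents suggests that seeing the PGA would act differently by arm.

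It is also fair to say that the visible text plans no analysis of agreement between PhGA and PGA, so no stated inference relies on their being independent. That limits the harm but does not remove the contradiction.

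**Conclusion.** The contradiction is real. Following Section 6.5.2 as written defeats the masking that Section 6.5.1.1.1 requires, at 11 scheduled visits and for up to 550 ratings.

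That count is an upper bound. It assumes that all 50 patients attend all 11 visits, that the same investigator reviews the questionnaires and scores the PhGA, and that the review includes the PGA. It measures exposure and is not an effect size; the documents give nothing from which anchoring could be estimated.

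The consequence is limited to how far the PhGA can be read as a rating made independently of the patient's own. The point is modest in impact, can be settled from the text, and is worth correcting because correction is cheap.

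**What to change.** Reconcile the two sections by amending Section 6.5.2 and the ordering bullets in Section 6:

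1. The patient completes all questionnaires.
2. The investigator carries out the pre-examination adverse-event review on FACIT-Fatigue, SF-36, EQ-5D and any written comments, without the PGA VAS.
3. The investigator who scores the PhGA enters it without having seen the PGA.
4. The PGA VAS is then released and reviewed at the same visit, before study drug is given. At Week 52, when no dose is scheduled, it is reviewed before the visit ends.

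The hold should apply only to PhGA scoring. The amendment should add no restriction to the GCA signs-and-symptoms assessment, the flare decision or the escape decision.

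The cost is a sentence in each section and a note to sites, with no additional staff or procedure. The one drawback is that a single VAS mark is read for possible adverse events slightly later in the same visit.
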